2.4 Endpoints

2.4.1 Primary Endpoints

Injection Pain: Each Subject will evaluate pain after completion of each pair of injections using a 15 cm relative Visual Analog Scale (VAS).

2.4.2 Secondary Endpoints

After each injection:

• Leakage: After saline delivery equivalent to 30U of U100 insulin (0.3mL) and subject removal of pen needle from body, study staff will use the provided materials and scale to absorb leakage from the pen needle tip and injection site to measure the amount of leakage.

Leakage will be considered to be present if measurement is equivalent to or greater than 5% of dose (equivalent to $\geq 0.015g$).

• Needle bending: Study staff will use a provided needle bend scale and visually inspect retained pen needles to determine the presence of bending. If present, study staff will determine and document degree of bend with the provided scale. For the purpose of answering the study objective, needle bend will be considered if the bend rating ≥ 2.

After each pair of injections:

• Injection force: Each subject will evaluate perceived injection force after each pair of injections using a 5-point Likert scale (from 1st injection required much less force to deliver medication to 2nd injection required much less force to deliver medication).

2.4.3 Exploratory Endpoints

During each injection: Injection time - includes the following time periods for each injection

- Time from when subject first pushes injection button to time button fully depressed (delivery time)
- Time from when injection button fully depressed to when pen needle removed from body
- Total injection time the 2 time periods above combined

After each injection:

• Breaking: Study Staff will record any patient end needle breakage. Breakage is defined as the patient-end metal cannula separated into two pieces.

After all injections completed:

- Survey responses: Subject completes a 5-point Likert scale survey (from Disagree to Agree). Subject will be instructed to respond to the questions based on their usual (in-home use) injection experience. Subject responses to survey questions will be tallied. The survey includes the following four questions:
 - 1. Injection pain affects my level of satisfaction with my treatment.
 - 2. Injection pressure needed to deliver the dose affects my level of satisfaction with my treatment.
 - 3. Post injection leakage increases my level of concern that I may not be receiving my full dose of medication.
 - 4. A bent needle increases my level of concern about the reliability of my injection.

2.4.4 Safety Endpoints

Occurrence of adverse events will be evaluated, recorded, and followed up as required.

2.5 Acceptance Criteria

2.5.1 Primary Objective

BD NanoTM PRO non-inferior to each comparator for injection pain with partially blinded injections based on relative VAS, where -75mm indicates worse pain for BD NanoTM PRO and +75mm indicates worse pain for comparator with a non-inferiority criterion of -10mm.

2.5.2 Secondary Objectives

- The BD Nano[™] PRO will be evaluated for superiority vs each comparator for leakage, injection force, and bending.
- If the BD Nano[™] PRO demonstrates non-inferiority for injection pain for the Primary Objective, compare the BD Nano[™] PRO vs each comparator for superiority.

2.5.3 Exploratory Objectives

No formal acceptance criterion has been established for the following objectives - time to deliver dose, total injection time, and survey responses after all injections completed.

3 Sample Size

Pain: Assuming the SD for relative VAS is around 50mm (based on DBC-17NUCLS07), a sample size of 266 pairs per each comparator has >90% power of passing a -10mm NI criteria, assuming no true difference in pain (based on a 2-sided 95% CI for the mean).

Leakage: Based on previous study data (BDT-2P00116) where leakage was greater than or equal to 1.5U was observed in 66/298 (22.1%) of injections performed with Artsana 34G, in 25/299 (8.4%) of injections performed with Comfort EZ 33G, in 19/296 (6.4%) of injections performed with Artsana 33G and in 3/297 (1%) of injections performed with BD NanoTM PRO, a simulation was performed (code found in SVN repository under DBC-18PENDL01/Sample Size/Bayesian prior proportion.R) indicating that 798 injections with BD NanoTM PRO and 266 injections per each comparator would provide >90% power to show BD NanoTM PRO superiority to each comparator. So the number of subjects needed is 133.

A 10% buffer was added (to compensate for subject attrition or unusable data), leading to a planned enrollment number of 146 subjects.

4 Intended Statistical Software

This document was generated with R version 3.5.1 (2018-07-02) and the following packages (version) were used: assertthat (0.2.0), base (3.5.1), BDbasics (0.2.4), bindr (0.1.1), bindrcpp (0.2.2), colorspace (1.3.2), compiler (3.5.1), crayon (1.3.4), datasets (3.5.1), dplyr (0.7.6), ggplot2 (3.1.1), glue (1.3.0), graphics (3.5.1), grDevices (3.5.1), grid (3.5.1), gtable (0.2.0), lattice (0.20.35), lazyeval (0.2.1), magrittr (1.5), methods (3.5.1), munsell (0.5.0), nlme (3.1.137), pillar (1.3.0), pkgconfig (2.0.2), plyr (1.8.4), purrr (0.2.5), R6 (2.2.2), Rcpp (0.12.18), reshape2 (1.4.3), rJava (0.9.10), rlang (0.2.2), scales (1.0.0), stats (3.5.1), stringi (1.1.7), stringr (1.3.1), tibble (1.4.2), tidyselect (0.2.4), tools (3.5.1), utils (3.5.1), withr (2.1.2), xlsx (0.6.1), xtable (1.8.3).

The analysis of this study will be conducted within the same environment or using more recent versions.

5 Data

5.1 Database Information

The input data will consist in several csv (comma separated values) files exported from Clindex.

Files will be saved in

https://svn.bdx.com:8443/svn/stats_and_dm/DM and Stats Outputs/DBC/DBC-18PENDL02/Data and read directly into R for analysis.

5.2 Analysis Population Set(s)

All data collected will be analyzed and reviewed for possible exclusion based on significant outliers or protocol deviations.

Injections where bleeding was observed will not be used in the leakage analyses.

Analyses of relative data will only include pairs where both injections were completed.

Demographic information and Diabetes history collected for all subjects randomized will be tabulated.

Data from all subjects will be included in the summary of safety parameters.

6 Statistical Analysis / Calculations

6.1 Derived Variables

6.1.1 Relative VAS Scale

After completion of each pair of injection, subjects will be asked to compare pain between the pen needles using a 150mm relative VAS Scale. Marks made on the 150mm relative VAS Scale are read using a 0 - 20 grid and the resulting discrete scores entered into the database. The results will be transformed to a [-75mm, 75mm] scale for analysis and reporting, where positive scores will reflect less pain for BD Nano Pro and negative scores will reflect less pain for comparator pen needle.

Subjects will draw a vertical line on a relative VAS scale for each pair of injections, to indicate their relative pain perception for the pen needle used first or second in the pair. A vertical line drawn to the left of the center mark indicates that the 1st injection was less painful. A vertical line drawn to the right of the center mark indicates that the 2nd injection was less painful. A vertical line drawn at the center mark indicates no difference. Figure 1 shows an example of a 150mm (may not be to scale) relative VAS scale.

Which injection was less painful?

The **1st injection** was much less painful.

No Difference

The **2nd injection** was much less painful.

Figure 1: VAS Scale for Injection Pain

The scores are entered into the database on a discrete 0 - 20 scale. These scores will be transformed to a 150mm VAS on a [-75mm, 75mm] scale as follows:

Let $Y_{recorded}$ (= 0, 1, ..., 20) be the recorded VAS score, the first transformation for the analysis of VAS score, $Y_{analusis}^*$ (mm), will be calculated as:

$$Y_{analysis}^* = \frac{150}{20} * Y_{recorded} - 75 \tag{1}$$

The sign of the VAS responses $Y_{analysis}^*$ will then be adjusted depending on which pen needle was used in the first and in the second injection, so that positive scores (+) will reflect less pain for BD Nano and negative scores (-) will reflect less pain for comparator pen needles. Let $Y_{analysis}$ be the final relative VAS score used for the analysis. Then:

$$Y_{analysis} = \begin{cases} Y_{analysis}^*, \text{ if BD Nano is provided in the 2}^{nd} \text{ injection} \\ -Y_{analysis}^*, \text{ if BD Nano is provided in the 1}^{st} \text{ injection} \end{cases}$$
(2)

6.1.2 Leakage Scale

Study Staff will use the provided materials and scale to absorb leakage from the pen needle tip and injection site to measure the amount of leakage. Leakage will be considered to be present if measurement is equivalent to or greater than 5% of dose (equivalent to equal to or greater than 1.5U of U100 insulin (or 0.015g)). A binary leakage variable will be created with the equation below:

$$Y_{Leakage} = \begin{cases} \text{Yes, if recorded leakage} \ge 0.015\text{g} \\ \text{No, if recorded leakage} < 0.015\text{g} \end{cases}$$
(3)

DBC-18PENDL02

6.1.3 Injection force

Injection force will be evaluated after each pair of injections using a 5-point Likert scale and the results will be converted to ratings of -2 to 2 as below:

$$Y_{Injectionforce}^{*} = \begin{cases} -2, \text{ if 1st injection significantly less thumb force} \\ -1, \text{ if 1st injection slightly less thumb force} \\ 0, \text{ if no difference} \\ 1, \text{ if 2nd injection slightly less thumb force} \\ 2, \text{ if 2nd injection significantly less thumb force} \end{cases}$$
(4)

The sign of the injection force responses $Y^*_{Injectionforce}$ will then be adjusted depending on which pen needle was used in the first and in the second injection, so that positive scores (+) will reflect less thumb force for BD Nano and negative scores (-) will reflect less thumb force for comparator pen needles. Let $Y_{Injectionforce}$ be the final injection force score used for the analysis. Then:

$$Y_{Injectionforce} = \begin{cases} Y_{Injectionforce}^*, & \text{if BD Nano is provided in the } 2^{\text{nd}} \text{ injection} \\ -Y_{Injectionforce}^*, & \text{if BD Nano is provided in the } 1^{\text{st}} \text{ injection} \end{cases}$$
(5)

The responses will also be converted to 3 categories: favoring comparator pen needle (negative ratings), no difference (0 ratings) and favoring BD NanoTM PRO (positive ratings) with the equation below:

$$Y_{Injection force(categorical)} = \begin{cases} \text{Comparator pen needle with less injection force if recorded rating} < 0\\ \text{No difference, if recorded rating} = 0 \\ \text{BD Nano with less injection force if recorded rating} > 0 \end{cases}$$
(6)

6.2 Analysis Method

This section provides a detailed description of the statistical analysis that will be performed in this study.

Unless otherwise stated, all the statistical tests are two-sided at a significance level of 5%.

Summary statistics (number of observations, mean, 95% CI for mean, median, standard deviation and range) for all quantitative responses will be presented in tables. Frequency tables with number of observations, percentage of total will be created for all discrete responses. If a modeling approach is applied, the fitted mean with 95% CI will be presented in tables.

Bar plots may be provided for some responses.

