### 2.2 Secondary Objectives

Demonstrate superiority of BD Nano™ PRO vs each of 3 comparator pen needles for the following:

- Leakage from the needle tip and the injection site (measurements combined) after removal from body
- Subject perceived force required to deliver dose
- Patient end needle bending after removal from body
- If primary outcome demonstrates non-inferiority then evaluate for superiority of BD Nano™ PRO vs each comparator.

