### Secondary Objectives:

- The BD Nano™ PRO will be evaluated for superiority vs each comparator, for leakage, thumb force, and bending
- If the BD Nano™ PRO demonstrates non-inferiority for injection pain for the Primary Objective, compare the BD Nano™ PRO vs each comparator for superiority.

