6.2.1 Analysis of Injection pain

For each comparator PN, a two-sided 95% confidence intervals will be calculated for the average rating. A modeling approach including data from all pairs of injections (all comparator PN included) will be used to analyze the data and estimate average ratings for each comparator PN adjusting for the pair order effect, BD order effect within pair (due to the often-observed bias towards favoring the last pen needle used in a pair), abdomen site effect, comparator PN effect and random subject effect. The interaction of PN and clinical site will be verified. If the interaction is significant, multiple comparisons for site difference by each PN will be conducted and results will be presented by site for PNs with significant site difference. If the interaction is not significant, it will be dropped from the model and clinical site will be included as main effect. If the site difference is significant, results will be presented by site for each PN. Otherwise, the site effect will be dropped from the model. Results will be tested for non-inferiority, followed by superiority:

- If the lower bound of the CI is > -10mm, we can conclude in non-inferiority.
- If the lower bound of the CI is > 0mm, we can conclude in superiority.

```
> ## Example for estimated pen needle subgroup means (Site effect not significant)
> ## if the lower CL is > -10, non-inferiority is satisfied
> ## if the lower CL is > 0, superiority is satisfied
> library(emmeans)
> emmeans(model.fit, ~Comparator)
```

Comparator	emmean	SE	df	lower.CL	upper.CL
Artsana 33G	26.87836	5.747502	140.26	15.515420	38.24129
Artsana 34G	20.09732	7.841233	139.57	4.594362	35.60027
Simple Diagnostics	22.40372	6.075449	140.25	10.392416	34.41502

Degrees-of-freedom method: kenward-roger Confidence level used: 0.95

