8.1.3 Executive Summary

A high level summary will be provided for each objective/endpoint (example below).

Primary Objective (examples only):

• *Injection Pain:* The lower bound of the CI for the average relative pain comparison between BD Nano[™] PRO and Artsana Insupen[®] 33G met both non-inferiority and superiority criteria.

Secondary Objectives (examples only):

- *Injection force:* The lower bound of the CI for the average difference in rating of BD Nano[™] PRO and Artsana Insupen[®] 33G injection force met the superiority criterion.
- *Needle Bending:* The upper bound of the CI for the average difference in percentage of needle bending occurrence with BD Nano[™] PRO and Artsana Insupen[®] 33G met the superiority criterion.
- Leakage: The upper bound of the CI for the average difference in percentage of leakage occurrence with BD Nano[™] PRO and Artsana Insupen[®] 33G met the superiority criterion.

In addition, a summary table for all primary and secondary objectives will be presented as in Table 3 (Example only). A blue check mark (\checkmark) indicates that the acceptance criterion is met, while a red X mark (\bigstar) indicates that the acceptance criterion is not met.

Objective	Comparison	
Primary Objective		
Injection Pain (Non-inferiority)	BD Nano vs Artsana 33G	 Image: A set of the set of the
Injection Pain (Non-inferiority)	BD Nano vs Artsana 34G	 Image: A set of the set of the
Injection Pain (Non-inferiority)	BD Nano vs Simple Diagnostics	 Image: A set of the set of the
Secondary Objective		
Injection Pain (Superiority)	BD Nano vs Artsana 33G	×
Injection Pain (Superiority)	BD Nano vs Artsana 34G	×
Injection Pain (Superiority)	BD Nano vs Simple Diagnostics	×
Injection force	BD Nano vs Artsana 33G	 Image: A set of the set of the
Injection force	BD Nano vs Artsana 34G	 Image: A set of the set of the
Injection force	BD Nano vs Simple Diagnostics	 Image: A set of the set of the
Needle Bending	BD Nano vs Artsana 33G	 Image: A set of the set of the
Needle Bending	BD Nano vs Artsana 34G	 Image: A set of the set of the
Needle Bending	BD Nano vs Simple Diagnostics	 Image: A set of the set of the
Leakage	BD Nano vs Artsana 33G	 Image: A set of the set of the
Leakage	BD Nano vs Artsana 34G	 Image: A set of the set of the
Leakage	BD Nano vs Simple Diagnostics	V

Table 3: Results Summar	v of	primary	and	secondary	v ob	jectives	Exam	ole	only)

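### Twelve secondary superiority marks are each decided on an unadjusted 95% CI with no multiplicity control: up to about a 26% chance of at least one false mark if no true difference exists

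*SAP*

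**What the plan says.** Protocol 2.2 states the aim as "Demonstrate superiority of BD Nano™ PRO vs each of 3 comparator pen needles for the following", followed by leakage, perceived force and bending. Pain is the fourth item and the only conditional one: "If primary outcome demonstrates non-inferiority then evaluate for superiority of" the test needle against each comparator. The acceptance criteria in Protocol 3.3 repeat this without a condition on the first three: "The BD Nano™ PRO will be evaluated for superiority vs each comparator, for leakage, thumb force, and bending".

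The level comes from SAP 6.2: "Unless otherwise stated, all the statistical tests are two-sided at a significance level of 5" percent. Each decision is made per comparator from its own two-sided 95% CI:

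- **Pain (SAP 6.2.1):** "Results will be tested for non-inferiority, followed by superiority", with the rule "If the lower bound of the CI is > 0mm, we can conclude in superiority".
- **Force (SAP 6.2.2):** the lower bound must exceed 0.
- **Bending and leakage (SAP 6.2.3):** the upper bound of the difference in proportions must be below 0%.

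SAP 8.1.3 promises that "a summary table for all primary and secondary objectives will be presented as in Table 3". That table has three non-inferiority rows and 12 superiority rows, each with its own mark. Neither document gives an adjustment, a split of alpha, a testing order across endpoints, or a gate from the primary objective to leakage, force or bending. The only multiple comparisons mentioned concern differences between clinical sites.

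**The concern.** The plan treats these 12 results as formal conclusions. They have acceptance criteria and pass or fail marks beside the primary, while Protocol 3.3 and SAP 2.5.3 give the time and survey endpoints no formal criterion. Leakage superiority was also part of the sample size case.

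A reader of Table 3 would take each check mark to carry a 2.5% one-sided risk of being wrong. That is true of a row chosen in advance. It is not true of whichever rows happen to pass out of 12, and a product claim could rest on any one of them.

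**Working it through.** **Inputs from the documents.** Two-sided 5% per test (SAP 6.2), so 2.5% for an error in favour of BD Nano PRO; four endpoints by three comparators (Protocol 2.2, SAP Table 3); pain SD 50 mm, 266 pairs per comparator, margin -10 mm; leakage 3/297, 19/296, 25/299 and 66/298, with 798 against 266 injections (Protocol 13.1).

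**Inputs assumed.** Correlations between tests are not given; the range used is 0 to 0.5.

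**1. The plan's own figures.**
- Pain non-inferiority power = Phi(10/(50/sqrt(266)) - 1.96) = Phi(3.26 - 1.96) = 90.4%. The stated figure of more than 90% reproduces.
- Leakage, with rates drawn from Beta(x+1, n-x+1) and an unpooled Wald interval: 89.8%, 97.5% and above 99.9%, against 90%, 98% and above 99% in Protocol Table 1. This reproduces, although the sponsor's prior and code are not shown.

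**2. Chance of at least one false superiority mark.**
- All 12 null, independent: 1 - 0.975^12 = 26.2%.
- Correlation within an endpoint only: 25.0% at 0.25 and about 23% at 0.5.
- Correlation 0.5 between all 12 tests: about 16%.
- Leakage truly superior, other nine null, independent: 1 - 0.975^9 = 20.4%.

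**3. The pain gate.** Per comparator it removes nothing: a lower bound above 0 mm is already above -10 mm on the same interval. If it meant non-inferiority against all three before any pain superiority, the chance of a false pain mark under independence would fall from 1 - 0.975^3 = 7.3% to about 0.073 x 0.904^2 = 6.0%. The 12-test figure would then be 1 - 0.975^9 x 0.940 = about 25%.

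**4. Effect of Holm over three comparators within each endpoint.**
- Each endpoint is held at 2.5%, so four endpoints give at most 4 x 2.5% = 10% (1 - 0.975^4 = 9.6% if independent).
- Adding a fixed order, moving on only when all three comparators pass, brings the whole set to 2.5%. A false mark at a later endpoint then requires every earlier hypothesis to have been rejected.
- Probability of all three leakage claims, by the method of step 1: about 88.0% unadjusted and about 87.9% with Holm. Testing would therefore stop at leakage about 12% of the time.

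**5. What gating everything on the primary would cost.** At the plan's assumptions, all three pain non-inferiority tests pass with probability 74%, 76% or 79% at between-comparator correlation 0, 0.25 or 0.5. If leakage is independent of pain, all-three leakage success becomes 0.88 x 0.74 to 0.88 x 0.79, or about 65% to 70%.

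**The case against.** **These are secondary endpoints, and the documents never call them confirmatory.** The word is indeed absent. The aim to demonstrate superiority, the acceptance criteria and the marks in Table 3 still make them formal claims.

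**The family of 12 is a choice.** The comparators are three separate products, and a family of four endpoints per product gives 1 - 0.975^4 = 9.6%. This is a fair alternative, but 9.6% is still well above 2.5%, and Table 3 reports all 12 together.

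**Superiority against each of three could mean that all three must pass.** The error under a global null would then be below 1%. The decision rules and the example tables work row by row, however: SAP Table 8 shows one fail and two passes within one endpoint.

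**26% is near a ceiling.** This stands. It needs all 12 nulls true and independent tests. The same subject rates pain and force on the same pair, and the sponsor's earlier leakage data (1% against 6.4% to 22.1%) argue against a null for leakage. A reader might also infer a firm floor of 23%, but that assumes uncorrelated endpoints.

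**Stronger remedies are tempting.** A reader might infer that every secondary test should wait for the primary, but step 5 shows what that costs. Nor can the order be taken as already fixed: SAP 2.2 lists leakage first, Table 3 lists it last, and neither is called a testing order.

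**Conclusion.** The concern holds. Twelve superiority conclusions are drawn with no multiplicity control. The chance of at least one false mark is at most about 26% under a global null, roughly 16% to 26% for assumed correlations of 0 to 0.5, and about 20% if leakage is truly superior and the other nine tests are independent nulls. Even 16% is more than six times the 2.5% that a single mark suggests.

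Three stronger readings are not supported:

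- **The primary objective is inflated.** It requires non-inferiority to each comparator, so it needs no adjustment.
- **The error is 46%.** That is 1 - 0.95^12, which counts errors in both directions; only those in favour of BD Nano PRO produce a superiority mark.
- **The time measures belong in the count.** Protocol 13.3 and SAP 6.2.4.1 do apply a superiority rule to two of them, but they have no formal acceptance criterion and no row in Table 3.

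The error figures rest on assumed correlations. The power figures rest on the earlier leakage data, a Wald interval and independent injections.

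**What to change.** In SAP 6.2 and Protocol 13.3, before database lock:

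1. Within each endpoint, apply Holm over the three comparators at one-sided 2.5%.
2. State one endpoint order, with leakage first because it is the secondary endpoint with a power calculation. Move to the next endpoint only if all three comparators pass.
3. After a stop, report estimates and 95% CIs but give no pass mark in Table 3.
4. Do not make leakage, force and bending conditional on all three pain non-inferiority tests.

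**Cost.** Only wording and the rule behind Table 3 change; no subjects, visits or data are added. All-three leakage power is essentially unchanged (about 88.0% to 87.9%). Later endpoints lose their formal claim if an earlier one fails, which happens about 12% of the time at the leakage step under the planning data.

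**Minimum, if the sponsor does not accept an order.** Use Holm within each endpoint, which limits the chance of any false mark to about 10%, and label the Table 3 marks as not controlled across endpoints.

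A single Holm procedure over all 12 tests would also control the error. Its price depends on the interval: if the other nine tests are null, leakage power against Artsana 33G falls from about 90% to about 71% with a Wald interval, and from about 94% to about 85% with a score interval.
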